### **6.5.2 Secondary Outcome Measures**

1. Cigarettes per day (CPD). The total number of cigarettes smoked each day will be assessed by the Quitbit lighter (see above). In addition, the Timeline Follow-back (TLFB) procedure will be used to assess the participants’ self-reported use of cigarettes, other tobacco products, alcohol and illicit substances for each day of the study. The CPD based on the TLFB will be used in statistical analyses in the event of Quitbit lighter problems for a given day.
2. Carbon monoxide (CO) level. CO in each participant’s breath will be tested using the Bedfont Micro+ Smokerlyzer® as outlined in Table 2. A CO level of  $\leq 8\text{ppm}$  will be used to verify reports of no smoking.
3. Nicotine withdrawal will be assessed with the Minnesota Nicotine Withdrawal Scale (MNWS), a self-assessment of the intensity (i.e., 0=none at all to 4=severe) with which the respondent is experiencing 8 nicotine withdrawal symptoms.
4. Opioid withdrawal will be assessed with the Subjective Opiate Withdrawal Scale (SOWS), a self-assessment of the intensity (i.e., 0=not at all to 4=extremely) with which the respondent is experiencing 16 opioid withdrawal symptoms.
5. Drug Effect Questionnaire (DEQ) - Subjective experience of methadone will be assessed with the 5-item DEQ, a PhenX Toolkit-recommended measure, in which participants rate the degree to which they experience 5 drug-related effects (i.e., feel a drug effect, high, like the drug, dislike the effect, would like more drug) by making a mark along a 100-mm line from 0 (not at all) to 100 (extremely).

### **6.5.3 Screening/Baseline Measures**

1. Smoking History Survey. The Smoking History Survey is a modified version of the Mayo Nicotine Dependence Center Patient Questionnaire. It asks participants how many CPD they smoke, at what age they started smoking, number of years smoking, how many times they have attempted to quit (including methods), when the last quit attempt occurred, their longest period of cigarette abstinence, and if there are other smokers in their household. Information on other non-cigarette tobacco products will also be noted.
2. The Fagerström Test for Nicotine Dependence (FTND) is a brief self-administered assessment of cigarette use patterns that yields a single overall dependence score.
3. Mini International Neuropsychiatric Interview, version 6.0 (MINI) will be administered by a trained interviewer to evaluate for the presence of exclusionary psychiatric disorders.
4. Blood Chemistries. During screening/baseline, blood will be collected in serum separation evacuated venous blood collection tubes. Quantitative analysis will be performed, which will include the following

analytes: glucose, creatinine, alanine aminotransferase (ALT/SGPT), aspartate aminotransferase (AST/SGOT), gamma glutamyltranspeptidase (GGT), and blood urea nitrogen (BUN). A prescription topical numbing cream may be offered to all participants prior to the blood draw.

5. Complete blood count (CBC). A CBC with differentials and platelet count will be performed during screening/baseline (from same blood draw as blood chemistries, above). Quantitative analyses for hemoglobin, hematocrit, red blood cells, platelets, total white blood cells, and percentage of neutrophils, lymphocytes, monocytes, eosinophils, and basophils will be performed.
6. Pregnancy Test and Birth Control Assessment. A urine pregnancy test designed to measure human chorionic gonadotropin hormone will be completed during screening. All female participants will be tested except women who have a documented hysterectomy. During screening/baseline, female participants' use of birth control and breastfeeding status will be assessed.
7. Urine drug screen (UDS). A rapid UDS system that screens for cocaine, methamphetamine, amphetamine, opioids, benzodiazepines, and marijuana will be used to analyze a screening/baseline urine sample. To avoid falsification, urine samples will be collected using temperature monitoring and the validity of urine samples will be checked with the use of a commercially available adulterant test.
8. ECG. Twelve-lead electrocardiograms will be performed during screening/baseline according to standard procedures. Ventricular rate (bpm), PR (ms), QRS (ms) and QTc (ms) will be reported on the ECG readouts. The results will be reviewed by a study physician for interpretation and for a clinical judgment about whether the participant is eligible for the study based on the ECG results.
9. Medical History. A medical history will be performed by a qualified medical staff member.
10. Physical Exam. Performance of a physical exam during screening/baseline will be done by a medical staff member qualified to perform physical exams.
11. Weight/Height. The participant's weight and height will be recorded during screening/baseline.
12. The Suicide Behaviors Questionnaire-Revised (SBQ-R) is a validated measure of suicidal behavior that will be completed by the participant during screening/baseline. A score  $\geq 8$  will trigger a suicidal risk assessment by a qualified mental health professional.
8. 13. Methadone Maintenance Treatment Status. Only patients who have been enrolled in the UCPC-OTP program for at least 30 days and stable on the current methadone dose for at least 1 week are eligible to participate (see section 6.4.1); clinic records will be used to verify this criterion.

#### **6.5.4 Safety Measures**

1. Vital Signs. Vital signs, including blood pressure and heart rate, will be assessed according to the schedule in Table 2. Systolic blood pressures greater than 160 or less than 90 and diastolic greater than 100 and less than 60 will be brought to the attention of a study physician for review.
2. Adverse Events (AEs). AEs will be assessed by study staff as outlined in Table 2. If an AE requires medical attention, it will be reported to a study physician immediately.

3. Prior/Concomitant Medications. All medications taken by the participant for the 30 days prior to screening/baseline, during screening/baseline, and during the active study will be documented on a Prior/Concomitant Medications assessment (see Table 2).

4. Abuse liability and subjective feeling of dependence associated with the NNS/PNS will be assessed using measures that were utilized in a study of the abuse liability of, and dependence on, the nicotine patch, gum, spray, and inhaler. Specifically, abuse liability will be assessed based on participant rating of the pleasantness/ unpleasantness and satisfaction of NNS/PNS compared with their usual cigarettes on a 9-point scale (1=very unpleasant/unsatisfying, 5=neutral, 9=very pleasant/satisfying). Subjective feeling of dependence will be assessed by participant rating of how dependent they feel on the NNS/PNS (1=definitely not, 2=possibly, 3=probably, and 4=definitely).

5. The Columbia Suicide-Severity Rating Scale (C-SSRS) is a validated assessment of suicidal ideation/ behavior; it will be completed following the schedule outlined in Table 2. An answer of yes to items 4 or 5 (suicidal intent or plan) will trigger a suicidal risk assessment by a qualified mental health professional.

## **6.5.5 Other Measures**

### **1. Demographics**

This assessment will include questions about the participant's ethnicity, age, and sex.

### **2. Medication adherence**

Adherence with using the NNS/PNS and varenicline/placebo as prescribed will be assessed with self-report. The participants will be provided with a log for tracking their use of the nicotine nasal spray. In addition, during study weeks 3, 4, 6, and 7, when participants are scheduled to take varenicline/placebo, they will be asked to bring their bottles to the methadone dosing window so that the first dose of the day can be observed. Finally, adherence with varenicline/placebo will be assessed with pill count. Participants will be provided with information packets for Nicotrol®NS and varenicline.

## **6.6 Randomization Plan**

Eligible participants will be randomized to receive the four interventions in one of four orders as outlined in Table 1, with 5 patients assigned to each order; this design will serve to mitigate potential order effects.

**Table 1. The four medication orders to which participants will be randomized**

	Week 1	Week 2	Week 3-4	Week 6-7
Order 1	PNS	NNS	Varenicline	Placebo
Order 2	PNS	NNS	Placebo	Varenicline
Order 3	NNS	PNS	Varenicline	Placebo
Order 4	NNS	PNS	Placebo	Varenicline

Note: PNS=Placebo Nasal Spray; NNS=Nicotine Nasal Spray

Allocation sequence generation: The list of treatment assignments will be randomly generated prior to study initiation, employing a permuted-block scheme to ensure an approximately equal number of participants in each treatment group at any time during recruitment. Random assignments will be generated using standard randomization procedures in SAS software, and the master list of assignments will be stored by a non-study

staff member, in a secure, locked location. The master list will be used to assemble treatment kits prior to study initiation.

Treatment assignment: When an eligible participant is ready to be randomized, the staff member will assign the participant the next available kit (e.g., the first randomized participant gets kit #01, the second randomized participant gets kit #02, etc.). The randomizing staff member will write the assigned kit number on the participant's randomization source document, and track all treatment assignments in a master log kept with the treatment kits.

## **6.7 Study Treatments**

As described in section 8.0, all participants will receive the four study medications: NNS, varenicline, and placebos. All participants will receive their methadone dose and counseling as typically provided by the opioid treatment program (OTP). For in-clinic doses, the timing of the methadone dose will be taken from the clinic record. For take home doses, participants will be instructed to call a secure study phone when they take their methadone dose to capture the time of the dose.

## **7.0 STUDY PROCEDURES**

### **7.1 Study Overview**

Table 2 provides an overview of the participant procedures and assessments.

### **7.2 Participant Recruitment and Consent**

Interested M-M patients who have been determined by telephone or face-to-face interview to smoke 10 or more CPD, report that they smoke the most in the 4 hour period following methadone dosing, and are likely to meet other eligibility criteria are invited to receive an explanation of the study purpose and requirements. If still interested after receiving a face-to-face explanation of the study, the candidate is given an opportunity to review, inquire about, and sign the informed consent form.

Any participant who has difficulty understanding the information contained in the consent form is asked to review the misunderstood portion(s) of the consent and discuss them with a research staff member until he or she shows complete understanding of the information and may thus give full consent. Research staff members work closely with the study candidates in an effort to help them understand the requirements of their participation. Persons with literacy problems are assisted to the extent possible. Any participant who is unable to demonstrate understanding of the information contained in the informed consent is excluded from study participation.

**Table 2 Overview of study assessments and procedures**

Assessment/ Procedure	Sern/ Base	Rand	Study Weeks							FU
			0	1	2	3	4	5	6	
NNS/PNS dispensed		X	X							
NNS/PNS taken			7X	7X						
Varenicline/Placebo dispensed				X	X		X	X		
Varenicline/Placebo taken					7X	7X		7X	7X	
Medication Adherence			X	X	X	X	X	X	X	X
Screening/Baseline										
Informed Consent	X									
Smoking History Survey	X									
Fagerström (FTND)	X									
MINI	X									
Blood chemistry	X									
CBC	X									
Birth Control Assessment	X									
Urine Pregnancy Test	X									
Urine for UDS	X									
Electrocardiogram	X									
Medical History	X									
Physical Exam	X									
Weight/Height	X									
Substance Abuse Tx Status	X									
SBQ-R	X									
Efficacy Assessments										
Quitbit cigarette lighter	7X	X	7X	7X	7X	7X	7X	7X	7X	
TLFB	X		X	X	X	X	X	X	X	X
SOWS	X		X	X	X	X	X	X	X	
Drug Effect Questionnaire	X		X	X	X	X	X	X	X	
MNWS	X		X	X	X	X	X	X	X	
CO level	X		X	X	X	X	X	X	X	X
Safety Assessments										
Vital Signs	X	X	X	X	X	X	X	X	X	X
Adverse Events	X	X	X	X	X	X	X	X	X	X
Prior/Concom Meds	X	X	X	X	X	X	X	X	X	X
Abuse liability			X	X						
Subjective dependence				X	X					
C-SSRS		X	X	X	X	X	X	X	X	X

Notes: “7X” represents a procedure or assessment performed each day of the week.

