### **7.4 Active Treatment Phase**

As outlined in Figure 1, the active treatment phase is 7 weeks in duration. During this time, participants will receive all four medications and will be scheduled for one research visit per week. Participants will be instructed not to smoke during medication evaluation weeks, which are study weeks 1, 2, 4 and 7. During medication evaluation weeks (i.e., Weeks 1, 2, 4, and 7) the research visits will be scheduled to occur during day 6 or 7 of the week in order to maximize participant exposure to the medication/placebo prior to assessment. All assessments ideally will be completed after the participant has received his/her methadone dose and before the participant smokes a cigarette, with the exception of the baseline visit when participants will be allowed to smoke prior to completing the assessments.

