### **8.11 Treatment Plan**

Table 4 delineates the dosing schedule and the weeks during which medication efficacy will be evaluated. All participants will use NNS/PNS during days 1-7 of study weeks 1 and 2 and will be instructed to utilize the spray and to not smoke during those weeks. Participants will be taught how to deliver a 0.5 mg spray in each nostril and will be instructed that they may use the spray up to 40 times a day but no more than 5 times an hour. Participants will undergo dose escalation of varenicline/placebo during study weeks 3 and 6, and will be on full dose during weeks 4 and 7. Participants who are unable to tolerate the target dose (2 mg/day) will be titrated to the highest dose tolerated. Participants will be instructed to not smoke during weeks 4 and 7, which are the weeks during which the efficacy of varenicline/placebo will be assessed. It should be noted that participants assigned to a medication order in which varenicline is given before varenicline placebo (i.e., orders 1 and 3 in Table 1), will have a two-week washout period before placebo is tested - the first week is the official "wash out" week during week 5 and the second is week 6 during which the participant is undergoing dose escalation for placebo.

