### 9.2 Analysis Plan

All analyses will be completed using SAS, Version 9.3 (SAS Institute, 2010).

1. Primary outcome analysis. The primary outcome analysis will consist of two sets of statistical analyses, one comparing the effect of NNS to PNS on the proportion of daily cigarettes smoked during the 4-hour post-methadone-dosing period and one comparing the effect of varenicline to placebo on the proportion of daily cigarettes smoked during the 4-hour post-methadone-dosing period. The statistical approach taken to both sets of analyses will be the same. A normal mixed model regression will include treatment (active vs. placebo) and the proportion of cigarettes smoked during the post-methadone-dosing period during baseline as covariates. In addition, corrected Akaike Information Criterion (AICC), will be used to determine whether treatment order (see Table 1), time (days 1-7), and / or the treatment-by-time interaction should be included as covariates in the mixed model regression. The dependent variable will be the proportion of daily cigarettes smoked during the 4-hour post-methadone-dosing period from the weeks during which the medication/placebo is being evaluated (see Table 2). The baseline urine drug screen result (positive or negative for substances other than opioids) will be controlled for in the analyses.

2. Secondary outcome analyses. The present trial has six secondary objectives, the analytic approach taken for each is described below. The baseline urine drug screen result (positive or negative for substances other than opioids) will be controlled for in the analyses.

2a. Preliminary evaluation of the ability of the NNS and varenicline, relative to placebos, to reduce total cigarettes per day (CPD). This secondary outcome analysis will consist of two sets of statistical analyses, one comparing the effect of NNS to PNS on CPD and one comparing the effect of varenicline to placebo on CPD. The analytic approach utilized for the primary outcome analysis will be used for this analysis with the variable of interest being CPD (i.e., as opposed to the proportion of daily cigarettes smoked during the post-methadone-dosing period).

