2b. Assessing the abuse liability of, and subjective feelings of dependence on, the NNS. The effect of NNS, compared to PNS, on the liability scale will be assessed using the same analysis procedure used for the primary outcome. The effect of treatment on the four-point dependence measure will be assessed with the same analysis procedure except that instead of a normal mixed model regression, a proportional odds logistic mixed model regression will be used.

2c. Exploratory analysis of the comparative efficacy of the NNS and varenicline in reducing cigarette smoking during the 4-hours post-methadone dosing period. The effect of NNS, compared to varenicline, on the proportion of daily cigarettes smoked during the 4-hour post-methadone-dosing period will be assessed using the same analysis procedure used for the primary outcome except that instead of comparing each experimental treatment to its respective placebo, the experimental treatments will be compared to each other. Because the order of NNS and varenicline is not counterbalanced (i.e., NNS is always received prior to varenicline), any significant differences may be due to an order effect and, thus, this is considered an exploratory analysis only.

2d. Exploratory analysis of the comparative efficacy of the NNS and varenicline in reducing total daily smoking in M-M patients. The analytic approach described in 2c will be used for this analysis with the variable of interest being CPD.

2e. Preliminary evaluation of the ability of the NNS and varenicline, relative to placebos, to decrease opioid and nicotine withdrawal. The analytic approach utilized for the primary outcome analysis will be used for these analyses with the variables of interest being SOWS total score and MNWS total score.

2f. Preliminary evaluation of the impact of the NNS and varenicline, relative to placebos, on the subjective experience of methadone. The analytic approach utilized for the primary outcome analysis will be used for these analyses with the variables of interest being each of the 5 items on the DEQ.

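### Table 2, as it reads, schedules the NNS/PNS dependence rating at weeks 2 and 3, one week later than the spray weeks, and does not say which spray each rating describes

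*Combined protocol and SAP*

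**What the plan says.** Secondary objective 2 (section 5.2) includes feelings of dependence on the NNS. Section 6.5.4, item 4, defines the measure: "Subjective feeling of dependence will be assessed by participant rating of how dependent they feel on the NNS/PNS", on a four-point scale. It names neither the spray (first or second) nor the recall period.

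Analysis 2b in section 9.2 states: "The effect of treatment on the four-point dependence measure will be assessed with the same analysis procedure", with a proportional odds mixed model in place of the normal one. The procedure it borrows takes its data "from the weeks during which the medication/placebo is being evaluated". For the sprays, Table 4 gives these as weeks 1 and 2.

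On dosing, section 8.11 says: "All participants will use NNS/PNS during days 1-7 of study weeks 1 and 2". Table 1 shows every participant changing spray between those two weeks. For the week after, section 8.11 says: "Participants will undergo dose escalation of varenicline/placebo during study weeks 3 and 6". Section 7.4 states that in evaluation weeks "the research visits will be scheduled to occur during day 6 or 7 of the week in order to maximize participant exposure".

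In Table 2, the row "Abuse liability" is marked in the same two columns as the row for NNS/PNS taken. The row "Subjective dependence" is marked one column further right.

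**The concern.** Analysis 2b is a crossover comparison. It needs one dependence rating per spray from each participant, made under similar conditions. With marks at weeks 2 and 3, no rating is made before the switch of spray. The first comes at the end of the second spray week, and the second comes when no spray is in use and tablets are being escalated. Depending on what a rating is taken to mean, the plan either loses the within-participant comparison or rates the first spray while the participant is using the other.

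Section 4.0 raises dependence on the spray as a particular concern in this population and describes this as the first NNS study in these smokers. A comparison that is imprecise, or pulled towards no difference, could be read as reassurance.

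**Working it through.** **1. Fixing the columns of Table 2.** The week header reads 0 to 6 and is damaged, so the columns have to be anchored to the text. Counting data columns from the left (1 = screening/baseline, 2 = randomization, 3 to 9 = weeks 1 to 7, 10 = follow-up):

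| Row | Columns marked | Weeks | Check |
|---|---|---|---|
| NNS/PNS dispensed | 2, 3 | randomization, 1 | agrees with 8.4 |
| NNS/PNS taken | 3, 4 | 1, 2 | agrees with 8.11 and Table 4 |
| Varenicline/placebo dispensed | 4, 5, 7, 8 | 2, 3, 5, 6 | consistent with the weeks taken |
| Varenicline/placebo taken | 5, 6, 8, 9 | 3, 4, 6, 7 | agrees with 6.5.5 and 8.11 |
| Abuse liability | 3, 4 | 1, 2 | the spray weeks |
| Subjective dependence | 4, 5 | 2, 3 | one column later |

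Taking the header literally would put dependence at weeks 1 and 2, but it would also put spray use at weeks 0 and 1, against section 8.11. A displaced header moves all rows together and cannot create an offset between rows.

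**2. What is rated when.** With 5 participants per order (section 6.6), orders 1 and 2 give 10 participants PNS then NNS, and orders 3 and 4 give 10 NNS then PNS. The week-2 visit is on day 6 or 7, after 5 to 7 days on the second spray. The week-3 visit is off spray. Week 3 is not an evaluation week, so the day 6 or 7 rule does not cover it.

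**3. Reading A: the rating means the current spray, or 2b uses evaluation-week data only.** Only the week-2 rating is usable. Of 40 ratings, 20 remain: 10 on NNS (orders 1 and 2) and 10 on PNS (orders 3 and 4). No participant has both, so all 20 pairs are lost.

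The plan gives no precision or power figure for dependence, so there is none to reproduce. As an illustration, take the proportions reporting dependency in section 8.8, 32% active and 13% placebo, a difference of 19 points.

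- 10 versus 10: 1.96 × √(.32×.68/10 + .13×.87/10) = 1.96 × √(.02176 + .01131) = .356, about 36 points.
- 20 pairs: 1.96 × √{[.2176 + .1131 − 2r√(.2176×.1131)]/20}. With assumed r = .3 this is .213; with assumed r = .5 it is .183. That is about 18 to 21 points.

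**4. Reading B: the rating means the previous week's spray.** Let N and P be the true mean ratings for NNS and PNS, and f the share of the week-2 answer that reflects the spray then in use. Assume the week-3 answer fully reflects the second spray.

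- Orders 1 and 2: N − [(1 − f)P + fN] = (1 − f)(N − P).
- Orders 3 and 4: [(1 − f)N + fP] − P = (1 − f)(N − P).

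The expected contrast is therefore (1 − f) of the true one: 100% at f = 0, 50% at f = .5 and 0% at f = 1. On the 19-point illustration that is 19, 9.5 and 0 points.

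**5. With ratings at weeks 1 and 2.** All 20 participants rate each spray at the end of its own week. This gives 20 NNS and 20 PNS ratings, paired, none made under the other spray or off spray.

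**The case against.** Three objections have weight.

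**The offset may come from PDF conversion.** It rests on two marks in one row of a table whose header is visibly damaged, and no prose section places dependence at weeks 2 and 3. A shift confined to that row cannot be ruled out from the text alone. It is unlikely, because the dosing rows all agree with the text, but the source table should be checked first.

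**The lag may be deliberate.** It follows each spray by one week in every order, and feeling dependent can sensibly be asked after stopping. Table 2 also marks medication adherence in the washout week and at follow-up, so marks after dosing are not unusual there. The measure is taken from a cited study whose timing is not available here. But no section states such an intention, and a deliberate lag would still have the first spray rated during use of the second.

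**The consequence is easily overstated.** A reader might infer that the comparison necessarily mixes the two sprays and that the difference disappears. The documents do not support this. Mixing arises only if ratings refer to the previous spray, and then only in the week-2 rating. A zero difference is the extreme case f = 1. If the form names the spray being rated, attribution may be clear; section 6.5.4 gives the scale and not the full item. The 32% and 13% come from other trials, with no duration of use stated, while here each spray is used for one week. The planned model is ordinal, so the half-widths are only illustrative.

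**Conclusion.** The point stands as an unexplained scheduling conflict in one secondary measure, subject to the check of the source table. As Table 2 reads, the dependence schedule does not fit the exposure rule in section 7.4 or the use of evaluation-week data that 2b inherits. The plan does not say which spray each rating belongs to.

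The size depends on that missing statement. Under Reading A, half the ratings and every pair are lost, and the illustrative half-width rises from 18 to 21 points to about 36, assuming correlations of .3 to .5 and the rates in section 8.8. Under Reading B, between all and none of the true contrast remains. Attenuation is towards no difference, given that the week-2 answer lies between the two sprays' true ratings, but its amount is unknown.

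Nothing here touches the primary outcome, cigarettes per day or the abuse-liability ratings, so it should not be read as a threat to the trial's main comparison. Nor do the documents establish that the marks are a typing slip. The correction is worth making in either case, since staff collect ratings by Table 2.

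**What to change.** First check the source of Table 2. If its dependence marks are already at weeks 1 and 2, the scheduling point closes.

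Otherwise, reconcile Table 2 with sections 6.5.4, 7.4 and 9.2:

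- Mark subjective dependence at weeks 1 and 2, at the same day 6 or 7 visits as abuse liability.
- In section 6.5.4, have each rating name the spray used that week.
- In analysis 2b, state that these two ratings per participant are the ones compared.
- If ratings after stopping are also wanted, keep the later ones as descriptive only, outside 2b, and state the spray and recall period for each.

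The cost is one row of Table 2 and a sentence in each of sections 6.5.4 and 9.2. The visits already exist, and moving the marks adds no assessment. Keeping the later ratings as well would add a single-item rating at existing visits.
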